Appendix 6: Diagnostic criteria for MS (2005 revision of McDonald Criteria)

Clinical presentation	Additional data needed for MS diagnosis
 ≥ 2 attacks Objective clinical evidence of 2 or more lesions 	• None
 ≥ 2 attacks Objective clinical evidence of 1 lesion 	 Dissemination in space¹, demonstrated by: MRI ≥ 2 MRI lesions consistent with MS + positive CSF or await further clinical attack implicating a different site
 • 1 attack • Objective clinical evidence of ≥ 2 lesions 	 Dissemination in time², demonstrated by: - MRI - or second clinical attack
 1 attack Objective clinical evidence of 1 lesion (monosymptomatic presentation; clinically isolated syndrome) 	 Dissemination in space¹, demonstrated by: MRI or ≥ 2 MRI lesions consistent with MS + positive CSF and Dissemination in time², demonstrated by: MRI or second clinical attack
• Insidious neurological progression suggestive of MS	 One year of disease progression and dissemination in space¹, demonstrated by two of the following: Positive brain MRI (≥ 9 T₂ lesions in brain), or ≥ 4 T₂ lesions in brain with positive visual evoked potentials, Positive spinal cord MRI (≥ 2 focal T₂ lesions), Positive CSF (oligoclonal IgG bands or increased IgG index).

¹ For MRI lesions disseminated in space, at least 3 of the following criteria must be met: one Gd+ lesion or 9 T₂-hyperintense lesions in the brain and spine, at least one infratentorial or spine lesion, at least one juxtacortical lesion, and at least 3 periventricular lesions.

² For MRI lesions disseminated in time, either of the following criteria must be met: Gd+ lesion \geq 3 months after initial presentation, but in different location from initial event; and new T₂ lesion, compared with reference MRI done \geq 30 days after onset of initial event.

CONFIDENTIAL - FOIA Exemptions Apply in U.S.

Ponesimod / ACT-128800 / JNJ-67896153 Multiple Sclerosis Protocol AC-058B202 Version 12 15 March 2022, page 158/179

Confidential

EudraCT 2009-011470-15 EDMS-ERI-206617631

Appendix 7: Kurtzke Expanded Disability Status Scale (EDSS)

	Neurological examination / Functional Systems (1)			
•	Pyramidal functions			
	\Box grade 0 =	Normal.		
	□ grade 1 =	Abnormal signs without disability.		
	\Box grade 2 =	Minimal disability (e.g., fatigability in motor tasks).		
	\Box grade 3 =	Mild or moderate paraparesis or hemiparesis; Or severe monoparesis.		
	□ grade 4 =	Marked paraparesis or hemiparesis; Or moderate quadriparesis; Or monoplegia.		
	\Box grade 5 =	Paraplegia, hemiplegia, or marked quadriparesis.		
	\Box grade 6 =	Quadriplegia.		
•	Cerebellar fu	inctions		
	\Box grade 0 =	Normal.		
	\Box grade 1 =	Abnormal signs without disability.		
	\Box grade 2 =	Mild ataxia.		
	\Box grade 3 =	Moderate truncal or limb ataxia.		
	\Box grade 4 =	Severe ataxia, all limbs.		
	\Box grade 5 =	Unable to perform coordinated movements due to ataxia.		
•	Brainstem fu	nctions		
	\Box grade 0 =	Normal.		
	\Box grade 1 =	Signs only.		
	\Box grade 2 =	Moderate nystagmus or other mild disability.		
	\Box grade 3 =	Severe nystagmus, marked extraocular weakness, or moderate disability of other cranial nerves.		
	\Box grade 4 =	Marked dysarthria or other marked disability.		
	\Box grade 5 =	Inability to swallow or speak.		

CONFIDENTIAL - FOIA Exemptions Apply in U.S.

Ponesimod / ACT-128800 / JNJ-67896153 Multiple Sclerosis Protocol AC-058B202 Version 12 15 March 2022, page 159/179 EudraCT 2009-011470-15 EDMS-ERI-206617631

Confidential

	Neurological examination / Functional Systems (2)			
•	Sensory functions			
	\Box grade 0 =	Normal.		
	\Box grade 1 =	Vibration or figure-writing decrease only, in one or two limbs.		
	\Box grade 2 =	Mild decrease in touch or pain or position sense, and/or moderate decrease in vibration in one or two limbs; Or vibratory (c/s figure-writing) decrease alone in three or four limbs.		
	\Box grade 3 =	Moderate decrease in touch or pain or position sense, and/or essentially lost vibration in one or two limbs; Or mild decrease in touch or pain and/or moderate decrease in all proprioceptive tests in three or four limbs.		
	\Box grade 4 =	Marked decrease in touch or pain or loss of proprioception, alone or combined, in one or two limbs; Or moderate decrease in touch or pain and/or severe proprioceptive decrease in more than two limbs.		
	\Box grade 5 =	Loss (essentially) of sensation in one or two limbs; Or moderate decrease in touch or pain and/or loss of proprioception for most of the body below the head.		
	\Box grade 6 =	Sensation essentially lost below the head.		
•	Bowel/bladd	er functions		
	\Box grade 0 =	Normal.		
	□ grade 1 =	Mild urinary hesitancy, urgency, or retention, and/or constipation.		
	\Box grade 2 =	Moderate urinary hesitancy, urgency, retention, or rare incontinence, and/or severe constipation.		
	\Box grade 3 =	Frequent urinary incontinence or intermittent self-catheterization, and/or severe bowel dysfunction.		
	\Box grade 4 =	In need of almost constant catheterization.		
	\Box grade 5 =	Loss of bladder function, external or indwelling catheter.		
	\Box grade 6 =	Loss of bowel and bladder function		

EudraCT 2009-011470-15

EDMS-ERI-206617631

Ponesimod / ACT-128800 / JNJ-67896153 Multiple Sclerosis Protocol AC-058B202 Version 12 15 March 2022, page 160/179

Neurological examination / Functional Systems (3) Visual (optic) functions • \Box grade 0 = Normal. \Box grade 1 = Mild scotoma and/or visual acuity of worse eye (corrected) better than 20/30 (0.67). \Box grade 2 = Worse eye with large scotoma and/or maximal visual acuity (corrected) of 20/30 to 20/59 (0.67-0.34). \Box grade 3 = Worse eye with large scotoma, or moderate decrease in fields, and/or maximal visual acuity (corrected) of 20/60 to 20/99 (0.33-0.2). \Box grade 4 = Worse eye with marked decrease of fields and/or maximal visual acuity (corrected) of 20/100 to 20/200 (0.1-0.2); Or grade 3 plus maximal acuity of better eye of 20/60 (0.3) or less. \Box grade 5 = Worse eye with maximal visual acuity (corrected) less than 20/200(0.1); Or grade 4 plus maximal acuity of better eye of 20/60 (0.3) or less. \Box grade 6 = Grade 5 plus maximal acuity of better eye of 20/60 (0.3) or less. Cerebral (or mental) functions • \Box grade 0 = Normal. \Box grade 1 = Mood alteration only (does not affect EDSS score). \Box grade 2 = Mild decrease in mentation. \Box grade 3 = Moderate decrease in mentation. \Box grade 4 = Marked decrease in mentation. \Box grade 5 = Dementia. **Other function** □ None. Any other neurological findings attributed to MS Please specify:

Confidential

EudraCT 2009-011470-15

Ponesimod / ACT-128800 / JNJ-67896153 Multiple Sclerosis Protocol AC-058B202 Version 12 15 March 2022, page 161/179

EDSS score 0 Normal neurological exam [all Grade 0 in Functional Systems (FS)]. 1.0 No disability, minimal signs in one FS (i.e., grade 1). 1.5 No disability, minimal signs in more than one FS (more than one grade 1). 2.0 Minimal disability in one FS (one FS grade 2, others 0 or 1). 2.5 Minimal disability in two FS (two FS grade 2, others 0 or 1). 3.0 Moderate disability in one FS (one FS grade 3, others 0 or 1), or mild disability in three or four FS (three/four FS grade 2, others 0 or 1) though fully ambulatory. Fully ambulatory but with moderate disability in one FS (one grade 3) and one or two FS grade 2; 3.5 or two FS grade 3; or five FS grade 2 (others 0 or 1). 4.0 Ambulatory without aid or rest for >500 m, up and about some 12 hours a day despite relatively severe disability consisting of one FS grade 4 (others 0 or 1), or combination of lesser grades exceeding limits of previous steps. 4.5 Ambulatory without aid or rest for >300 m, up and about much of the day; characterized by relatively severe disability usually consisting of one FS grade 4 or combination of lesser grades exceeding limits of previous steps. 5.0 Ambulatory without aid or rest for >200 m (usual FS equivalents are one grade 5 alone, others 0 or 1, or combination of lesser grades usually exceeding specifications for step 4.5). 5.5 Ambulatory without aid or rest for >100 m. Unilateral assistance (cane or crutch) required to walk at least 100 m with or without resting. 6.0 Constant bilateral assistance (canes or crutches) required to walk at least 20 m without resting. 6.5 Unable to walk 5 m even with aid, essentially restricted to wheelchair; wheels self and transfers 7.0 alone; up and about in wheelchair some 12 hours a day. 7.5 Unable to take more than a few steps; restricted to wheelchair; may need some help in transfer. 8.0 Essentially restricted to bed or chair or perambulated in wheelchair, but out of the bed most of the day; retains many self-care functions; generally has effective use of arms. 8.5 Essentially restricted to bed much of the day; has some effective use of arm(s); retains some selfcare functions. 9.0 Helpless bed patient; can communicate and eat. 9.5 Totally helpless bed patient; unable to communicate effectively or eat/swallow. 10.0 Death due to MS.

EDMS-ERI-206617631

Confidential

Ponesimod / ACT-128800 / JNJ-67896153 Multiple Sclerosis Protocol AC-058B202 Version 12 15 March 2022, page 162/179

Confidential

Appendix 8: Prohibited anti-arrhythmic and HR-lowering therapy

The following anti-arrhythmic drugs are prohibited during the titration (i.e., during the first 14 days after re-initiation of study treatment). [See Section 3.4.4.3 *Prohibited concomitant medications.*]

- Adenosine
- Acetobulol
- Ajmaline
- Amiodarone
- Aprinidine
- Atenolol
- Azimilide
- Bepridil
- Betaxolol
- Bisiprolol
- Bretylium
- Bunaftine
- Carvidiol
- Cibenzoline
- Disopyramide
- Dofetilide
- Dronedarone
- Encainide
- Esmolol
- Flecainide
- Ibutilide
- Ivabradine

- Lidocaine
- Lorajmine
- Lorcainide
- Metoprolol
- Mexiletine
- Morcizine
- Nadolol
- Phenytoin
- Pilocarpine
- Prajmaline
- Procainamide
- Propafenone
- Propranolol
- Quinidine
- Sotalol
- Sparteine
- Tedisamil
- Timolol
- Tocainide
- Vernakalant

This list is not exhaustive; other anti-arrhythmic or HR-lowering drugs are also prohibited during uptitration. In case of doubt, please discuss with the sponsor the use of any potential anti-arrhythmic or HR-lowering drug.

Treatment with any of these therapies is also not recommended during maintenance treatment with ponesimod (i.e., 20 mg) and should be considered with caution if an alternative medication cannot be used.

EudraCT 2009-011470-15 EDMS-ERI-206617631

EudraCT 2009-011470-15

EDMS-ERI-206617631

Ponesimod / ACT-128800 / JNJ-67896153 Multiple Sclerosis Protocol AC-058B202 Version 12 15 March 2022, page 163/179

Confidential

Appendix 9: List of medications with risk of torsades de pointes (TdP)

The use of the following QT-prolonging medications with risk of TdP is prohibited during the study unless the benefit-risk is acceptable, as judged by the investigator.

- Amiodarone
- Anagrelide
- Arsenic trioxide
- Astemizole
- Azithromycin
- Bepridil
- Chloroquine
- Chlorpromazine
- Cilostazol
- Ciprofloxacin
- Cisapride
- Citalopram
- Clarithromycin
- Cocaine
- Disopyramide
- Dofetilide
- Domperidone
- Donepezil
- Dronedarone
- Droperidol
- Erythromycin
- Escitalopram
- Flecainide
- Fluconazole

- Gatifloxacin
- Grepafloxacin
- Halofantrine
- Haloperidol
- Ibutilide
- Levofloxacin
- Levomethadyl
- Mesoridazine
- Methadone
- Moxifloxacin
- Ondansetron
- Pentamidine
- Pimozide
- Probucol
- Procainamide
- Propofol
- Quinidine
- Sevoflurane
- Sotalol
- Sparfloxacin
- Sulpiride
- Terfenadine
- Thioridazine
- Vandetanib

Ponesimod / ACT-128800 / JNJ-67896153 Multiple Sclerosis		EudraCT 2009-011470-15 EDMS-ERI-206617631
Protocol AC-058B202	Confidential	
Version 12		
15 March 2022, page 164/179		

The above list is based on the one published by AZCERT (October 2015) [AZCERT]. Any marketed drugs with new reported TdP or new marketed drugs with risk of TdP in their labels should not be administered unless the benefit-risk is acceptable, as judged by the investigator.

Reference for Appendix 9

[AZCERT] University of Arizona CERT. List of QT-prolonging medications with risk of TdP. Available under: www.AZCERT.org; www.QTdrugs.org [Accessed October 2015]

Ponesimod / ACT-128800 / JNJ-67896153 Multiple Sclerosis Protocol AC-058B202 Version 12 15 March 2022, page 165/179

Confidential

EudraCT 2009-011470-15 EDMS-ERI-206617631

Appendix 10: Guidance on study conduct during the COVID-19 (coronavirus) pandemic

It is recognized that the Coronavirus Disease 2019 (COVID-19) pandemic may have an impact on the conduct of this clinical study due to, for example, self-isolation/quarantine by participants and study site personnel; travel restrictions/limited access to public places, including hospitals; study site personnel being reassigned to critical tasks.

In alignment with recent health authority guidance, the sponsor is providing options for study-related participant management in the event of disruption to the conduct of the study. This guidance does not supersede any local or government requirements or the clinical judgment of the investigator to protect the health and well-being of participants and site staff. If at any time a participant's safety is considered to be at risk, study intervention will be discontinued, and study follow-up will be conducted.

Scheduled visits that cannot be conducted in person at the study site will be performed to the extent possible remotely/virtually or delayed until such time that on-site visits can be resumed. At each contact, participants will be interviewed to collect safety data. Key efficacy endpoint assessments should be performed if required and as feasible. Participants will also be questioned regarding general health status to fulfill any physical examination requirement.

Every effort should be made to adhere to protocol-specified assessments for participants on study intervention, including follow up. Modifications to protocol-required assessments may be permitted via COVID-19 Appendix after consultation with the participant, investigator, and the sponsor. Missed assessments/visits will be captured in the clinical trial management system for protocol deviations. Discontinuations of study interventions and withdrawal from the study should be documented with the prefix "COVID-19-related" in the case report form (CRF).

The sponsor will continue to monitor the conduct and progress of the clinical study, and any changes will be communicated to the sites and to the health authorities according to local guidance. If a participant has tested positive for COVID-19, the investigator should contact the sponsor's responsible medical officer to discuss plans for study intervention and follow-up. Modifications made to the study conduct as a result of the COVID-19 pandemic should be summarized in the clinical study report.

GUIDANCE SPECIFIC TO THIS PROTOCOL:

Patient Visits and Assessments

Assessments that may be completed over the phone include assessment of relapse, review of adverse events and concomitant medications. Vital signs can be collected in a remote setting by the patient, caregiver, delegated site staff/in-home nurse, or general practitioner,

Ponesimod / ACT-128800 / JNJ-67896153 Multiple Sclerosis		EudraCT 2009-011470-15 EDMS-ERI-206617631
Protocol AC-058B202	Confidential	
Version 12		
15 March 2022, page 166/179		

as feasible. Please ensure the remote method you choose is allowable per local regulations and fully documented in the patient source files.

It is important for safety monitoring of laboratory parameters to continue according to the protocol schedule. If access to the study site (and therefore the central lab) is not possible, local laboratories may be used to monitor laboratory parameters. An alternative, if allowed per local regulations, is to use delegated site staff/in-home nursing to collect blood samples at the patient's home and ship to either the central laboratory or an accredited local laboratory for testing. Where local laboratories are used, it's important to ensure appropriate documentation of laboratory reference ranges. If abnormal laboratory values requiring follow-up in the protocol, or any other abnormality deemed critical by the investigator, are unable to be followed up, it is recommended to temporarily interrupt (for a maximum of 12 weeks) until the abnormality can be considered resolved or permanently discontinue study treatment.

Other protocol-required examinations and assessments not conducive to remote administration can be conducted as soon as it is feasible for the patient to come to the site for a visit. As clinically indicated, other local resources such as the patient's general practitioner or delegated site staff/in-home nursing can be considered.

Study Drug Dispensation

If a patient is unable to travel to the site for a scheduled visit where study drug would be dispensed, the following alternate measures should be discussed with the sponsor and may be considered to ensure continuity of treatment:

- A caregiver or family member may pick up study drug on behalf of the patient if first discussed and agreed by the patient. The conversation with the patient must be documented in the source files. The patient must name the individual who will pick up study drug on their behalf. This is necessary for site staff to confirm the study drug is provided to the appropriate individual, ensure proper chain of custody of study drug, and to maintain patient privacy. This must be confirmed and documented in the patient source file.
- Investigative site staff may deliver study drug directly to the patient's home. The chain of custody and transit conditions must be clearly documented within the patient source file.
- If no other alternative is feasible, direct-to-patient shipment of study drug from the site may be considered with prior approval from the sponsor and relevant health authority, as applicable.
- It is important to remind patients that in case of treatment interruption of 4 or more consecutive days, they should inform the investigator and/or site staff immediately.

Ponesimod / ACT-128800 / JNJ-67896153 Multiple Sclerosis		EudraCT 2009-011470-15 EDMS-ERI-206617631
Protocol AC-058B202	Confidential	
Version 12		
15 March 2022, page 167/179		

Ponesimod treatment can only be restarted with uptitration and on-site cardiac monitoring, as applicable, as described in the protocol.

COVID-19 Infection in MS Patients:

There is currently no available data suggesting that patients treated with ponesimod should have treatment interrupted during the COVID-19 pandemic. In general, patients receiving immunomodulators should continue treatment and continue to exercise precautionary measures to minimize the risk of infection. If a patient develops symptoms associated with coronavirus infection, it is recommended to confirm the diagnosis using locally approved laboratory kits and reported to the local health authorities, as required. Patients with positive test results for coronavirus should have this recorded as an AE, and if hospitalized, this should be reported as an SAE. It is important to notify the treating physician of the patient's participation in this clinical study and details of the study treatment. It is also recommended to follow local MS Society recommendations.

On-site Monitoring Visits:

In case on-site monitoring visits are not possible, your monitor may arrange remote site monitoring activities with you until the point at which regular on-site monitoring visits may resume.

All of the above measures are recommended for consideration on a temporary basis during the COVID-19 pandemic to enable continuity of treatment and to ensure that patient assessments, particularly those assessing relapse and safety, continue as outlined in the protocol without imposing health risk to patients, their families, and site staff. Every effort should be made to complete all protocol-required assessments. Investigators should use their clinical judgment and benefit risk assessment in determining if a patient can continue study treatment in the absence of on-site clinic visits. If remote visits are not possible, or if in the investigator's judgment, appropriate safety monitoring is not feasible in a remote setting, the investigator should consider temporarily interrupting study treatment (for a maximum of 12 weeks per protocol) or discontinuing study treatment and initiating treatment with another available disease modifying treatment (DMT).

STUDY CONDUCT RELATED TO COVID-19 VACCINE DEPLOYMENT FOR NONCOVID-19 CLINICAL TRIALS

Current guidelines from global MS societies recommended that people with MS should be vaccinated against COVID-19.^{1,2,3} Having MS does not increase the risk of COVID-19 virus infection or the risk to develop severe forms of the infection more than the general population and it is important that DMT in MS patients is continued and maintained.⁴ It is therefore recommended that people with MS currently taking a DMT, including ponesimod, continue with their treatment unless advised to stop by their treating physicians (e.g., MS patients on DMT with risk factors for severe COVID-19 infections).

Ponesimod / ACT-128800 / JNJ-67896153 Multiple Sclerosis Protocol AC-058B202 Version 12 15 March 2022, page 168/179

Confidential

EudraCT 2009-011470-15 EDMS-ERI-206617631

No clinical data are available on the efficacy and safety of vaccinations in patients taking ponesimod.

Based on preclinical data, vaccinations may be less effective if administered during treatment.

There are 4 main types of COVID-19 vaccines (all non-live) that are currently available (see below). For a complete overview of the COVID-19 vaccine landscape, please refer to the WHO website.⁵

- **mRNA vaccines** are based on the SARS-CoV-2 spike glycoprotein antigen encoded by RNA and formulated in lipid nanoparticles;
- **Protein subunit vaccines** based on full-length spike protein (S), receptor-binding domain (RBD), non-RBD S protein fragments, and non-S structural proteins;
- Vector vaccines consisting of a recombinant adenovirus carrying the gene for SARS-CoV-2 virus spike glycoprotein;
- **Inactivated vaccines** use viruses whose genetic material has been destroyed so they cannot replicate, but can still trigger an immune response.

As stated in Section 3.4.4.2, vaccination with non-live vaccines is allowed while on study treatment if the vaccination is advised by the primary investigator / treating neurologist, based on her/his clinical assessment of the risk/benefit for the individual patient, and if supported by guidelines for vaccination relevant to this patient population, as applicable.

Therefore, all above mentioned COVID-19 vaccines may be administered to study patients.

Important notes and reminders:

- Vaccination with live vaccines is prohibited, except if performed during a temporary treatment interruption period. In this case it must be performed not earlier than 1 week after the last dose of study treatment, and treatment can be re-initiated only after at least 4 weeks from completion of vaccination (see Section 3.4.4.3).
- Patients receiving non-live vaccination against influenza or COVID-19 while on study treatment will have 5 mL of blood drawn prior to and at least 3 weeks after vaccination to explore changes in vaccine-specific antibody titers from pre- to post vaccination. Samples will be analyzed at the end of the study at the latest (see Section 3.11.2.9).
 - In case of a vaccine requiring the administration of multiple doses, the postvaccination sample should be collected at least 3 weeks after the administration of the last dose.
 - Every effort should be made to collect these samples for further analysis.
- Please report any administered vaccines on a Concomitant Medication page in the CRF.

Ponesimod / ACT-128800 / JNJ-67896153EudraCT 2009-011470-15Multiple SclerosisEDMS-ERI-206617631Protocol AC-058B202ConfidentialVersion 1215 March 2022, page 169/179

If a patient is eligible for COVID-19 vaccination in accordance with their local regulations their participation in the study should be modified as required.

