Protocol AC-058B202	Confidential	
Version 12		
15 March 2022, page 142/179		

F) Liver abnormalities

In the event of abnormal liver tests or signs and symptoms suggestive of drug induced liver injury (DILI), the patient will be closely observed, liver tests will be repeated, and study treatment discontinuation should be considered according to the guidance provided in Table 8.

Note: All events of ALT or AST $\geq 3xULN$ and total bilirubin $\geq 2xULN$ (>35% direct bilirubin) or ALT or AST $\geq 3xULN$ and INR >1.5 may indicate severe liver injury (possible 'Hy's Law') and must be reported to sponsor in an expedited manner and as an SAE if SAE criteria are met. The INR stated threshold value will not apply to patients receiving anticoagulants.

EudraCT 2009-011470-15

EDMS-ERI-206617631

Ponesimod / ACT-128800 / JNJ-67896153 Multiple Sclerosis Protocol AC-058B202 Version 12 15 March 2022, page 143/179

Confidential

Table 8:Guidance for patient monitoring and discontinuation for liver enzyme
abnormalities

Item	Laboratory parameter	Guidance
1	ALT or AST ≥ 3 × ULN *	Start close observation. Repeat labs within 72 hours. See items 1a and 1b. * if ALT or AST \ge 8 × ULN OR ALT or AST \ge 3 × ULN and TBL \ge 2 × ULN or INR > 1.5 ^a OR ALT or AST \ge 3 × ULN with the appearance of fatigue, nausea, vomiting, right upper quadrant pain or tenderness, fever, rash, and/or eosinophilia (> 5%) and retest cannot be done within 72 hours, permanently discontinue study treatment, and perform FU.
1a	If at repeated labs, ALT or AST \ge 3 × ULN < 8 × ULN	Continue close observation. Repeat labs twice weekly. See items 2a and 2b.
1b	If at repeated labs, ALT or AST <3 × ULN	Resume regular labs schedule.
2a	If at repeated labs, ALT or $AST \ge 5 \times ULN$ for > 2 weeks	Permanently discontinue study treatment, and perform FU.
2b	If at repeated labs, ALT or AST \ge 3 × ULN <5 × ULN for > 2 weeks	Continue close observation. Repeat labs once or twice weekly.
3	 If at repeated labs: ALT or AST ≥ 8 × ULN ALT or AST ≥ 3 × ULN and TBL ≥ 2 × ULN or INR > 1.5^a ALT or AST ≥ 3 × ULN with the appearance of fatigue, nausea, vomiting, right upper quadrant pain or tenderness, fever, rash, and/or eosinophilia (> 5%) 	Permanently discontinue study treatment, and perform FU.

ALT alanine aminotransferase; AST aspartate aminotransferase; FU follow up; INR International Normalized Ratio; TBL total bilirubin; ULN upper limit of normal range.

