^a Note: All events of ALT or AST \geq 3xULN and total bilirubin \geq 2xULN (>35% direct bilirubin) or ALT or AST \geq 3xULN and INR >1.5 may indicate severe liver injury (possible 'Hy's Law') and must be reported to sponsor in an expedited manner and as an SAE if SAE criteria are met. The INR stated threshold value will not apply to patients receiving anticoagulants.

Ponesimod / ACT-128800 / JNJ-67896153 Multiple Sclerosis		EudraCT 2009-011470-15 EDMS-ERI-206617631
Protocol AC-058B202	Confidential	
Version 12		
15 March 2022, page 144/179		

Whenever AST or ALT $\ge 3 \times$ the upper limit of normal range (ULN) are recorded by the central laboratory, an alert will be sent to the principal investigator and the sponsor. The sponsor will contact the principal investigator to ensure that she/he will immediately contact the patient, and ask the patient about any potential symptoms. The patient will be closely observed and will be asked to return to the site as soon as possible after the time of receipt of the alert to repeat the liver enzyme and bilirubin tests by the central laboratory (unless the clinical situation mandates immediate local testing) according to the scheme illustrated in Table 8. Further diagnostic work-up and consultation with a hepatologist or other specialist should be considered, and adequate medical management should be provided according to local practice and the clinical situation. Any clinically relevant finding meeting the definition of an AE will be recorded accordingly in the CRF.

In the event of study treatment interruption, the patient will be closely observed and FU liver tests will be performed. Following study treatment interruption, if liver tests normalize and drug related hepatotoxicity is unlikely, study treatment may be re-initiated at the discretion of the investigator. The decision to permanently discontinue study treatment will be made after evaluation of all available information concerning concomitant medications, other potential causes of hepatotoxicity, and the clinical status of the patient. Note: The re-initiation is not permitted for situations where the study treatment should be permanently discontinued according to Table 8. In all cases of permanent study treatment discontinuation, FU monitoring must be provided until signs and symptoms have resolved and changes in liver function are no longer regarded as clinically relevant or until medically indicated.

Reference for Appendix 1

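### Appendix 10 allows interruption when an abnormal laboratory value cannot be followed up, but for three Table 8 liver patterns Appendix 1 allows only permanent discontinuation, and no text says which prevails

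*Protocol*

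**What the plan says.** **Appendix 10 (Covid-19 guidance, patient visits and assessments).** The trigger is broad: "If abnormal laboratory values requiring follow-up in the protocol, or any other abnormality deemed critical by the investigator". If such a value cannot be followed up, the first option is interruption, "unable to be followed up, it is recommended to temporarily interrupt (for a maximum of 12 weeks) until the abnormality can be considered resolved", and the sentence ends "until the abnormality can be considered resolved or permanently discontinue study treatment". The closing part of the pandemic guidance repeats the pair for patients who cannot be monitored remotely: "temporarily interrupting study treatment (for a maximum of 12 weeks per protocol) or discontinuing study treatment".

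**Appendix 1, section F and Table 8.** For ALT or AST of at least 3 × ULN the default in item 1 is "Start close observation. Repeat labs within 72 hours. See items 1a and 1b". A starred note then picks out three patterns:

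- ALT or AST ≥ 8 × ULN;
- ALT or AST ≥ 3 × ULN with total bilirubin ≥ 2 × ULN or INR > 1.5;
- ALT or AST ≥ 3 × ULN with listed symptoms or eosinophilia.

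For these, if "retest cannot be done within 72 hours, permanently discontinue study treatment, and perform FU". The text that follows the table, not the table itself, adds: "The re-initiation is not permitted for situations where the study treatment should be permanently discontinued according to Table 8".

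**Section 3.6.1** makes discontinuation mandatory when an Appendix 1 criterion is met. **Section 3.6.2** caps interruptions for reasons other than planned pregnancy at 12 weeks, which agrees with Appendix 10.

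**The concern.** Both texts speak to the same event: a laboratory abnormality whose repeat test cannot be obtained. For the three starred patterns one text offers two actions and the other offers one. A site that picks interruption is following Appendix 10 and departing from a stopping rule in Appendix 1. Two sites, each able to point to the protocol, could manage the same patient differently. The patterns include a combination that section F itself flags as possible severe liver injury.

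There is a smaller reporting consequence. Under SAP Sections 5.4.3.8 and 5.4.3.9 the action recorded for the event decides whether it counts as leading to discontinuation or to temporary interruption. The first kind is tabulated (Section 5.4.4.4.3); the second is only listed (Section 5.4.4.4.4). Treatment disposition (Section 5.2.1.5), the interruption-based compliance measure (Section 5.4.1.2) and the count of Covid-19-related discontinuations (Section 5.5.8) would also differ.

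**Working it through.** No sample size, error rate or event count is involved, so the check is a comparison of texts. The question for each kind of abnormality is what each appendix allows when follow-up cannot be done.

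| Abnormality | Appendix 10 | Appendix 1, section F | Result |
|---|---|---|---|
| Starred Table 8 item 1 patterns | Interrupt up to 12 weeks, or discontinue | Discontinue permanently; restart barred | Interruption conflicts; discontinuation agrees |
| ALT or AST ≥ 3 and < 8 × ULN, with none of the bilirubin, INR, symptom or eosinophilia criteria | Same two options | Observation and repeat testing; no permanent stop tied to a missed repeat | No conflict |
| Non-liver values | Same two options | Table 8 does not apply | No conflict with Table 8 |

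Three further points were checked.

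1. *Scope of the 72-hour clause.* The layout leaves unclear whether it qualifies all three starred patterns or only the last. If all three, permanent discontinuation follows from the missed retest in each. If only the last, the first two call for permanent discontinuation whether or not a retest is possible. The conflict exists under both readings.
2. *Force of Table 8.* The opening of section F is soft: it calls the table guidance under which discontinuation should be considered. The table entry is imperative, the restart bar is worded as a prohibition, and Section 3.6.1 says must. (The examples named in Section 3.6.1 do not include liver tests, but the list is introduced as non-exhaustive and section F belongs to Appendix 1.)
3. *Precedence.* The opening of Appendix 10 preserves local or government requirements and the investigator's clinical judgment. It does not mention the Appendix 1 criteria. The amendment table shows that Amendment 8 introduced both the pandemic guidance and the liver guidance, yet the current text does not link them.

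**The case against.** The best reply is that the texts can be read together. Appendix 10 is a general recommendation with two options; Appendix 1 is a specific criterion that Section 3.6.1 makes mandatory. On ordinary principles the specific rule governs, and a site satisfies both by discontinuing. The restart bar is not limited by the reason for an interruption, and nothing in Appendix 10 lifts it. Appendix 10 also says that study treatment will be discontinued if a participant's safety is considered to be at risk. Where the site cannot be reached it offers local laboratories or home blood collection, so the disputed sentence matters only when those fail too. The sponsor is alerted to every central-laboratory ALT or AST result of at least 3 × ULN and contacts the investigator, which limits divergence between sites.

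Most of this stands, and it reduces the number of cases. It does not remove the conflict: the rule that the specific text prevails is sensible but is not written down, and the safety sentence depends on judgment and does not point to Table 8.

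Some stronger readings are not supported. A reader might infer that Appendix 10 recommends interruption alone; it offers discontinuation in the same sentence. A reader might infer that the appendix permits stopping rules to be modified; its modification clause concerns assessments, after consultation with the participant, the investigator and the sponsor. A reader might also take every liver alert to be affected; only the starred patterns are.

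**Conclusion.** The inconsistency is real and narrow. For the three starred patterns, when the retest cannot be done within 72 hours, the interruption option in Appendix 10 is incompatible with Table 8 and with the restart bar. The discontinuation option is compatible. The passages need to be reconciled.

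The size cannot be computed. The documents do not say how many patients reached a starred pattern, or how many of those could not be retested; given the sampling alternatives, the number is probably small. It is tempting to use the 19.5% of ponesimod 20 mg patients with increased ALT in the Phase 3 study (Section 1.3.2.4). That figure counts any such adverse event in another study and does not measure these cases. The same section describes transaminase rises on ponesimod as asymptomatic and without a bilirubin increase, which suggests that two of the three patterns are uncommon.

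The point earns a correction because it touches a safety stopping rule and is cheap to close, not because any exploratory result is shown to change. It assumes that a site reads Appendix 10 as written, without supplying a precedence rule. It takes no view on which clinical rule is right.

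**What to change.** Reconcile the laboratory paragraph of Appendix 10 with Table 8, the restart text in section F of Appendix 1, and Section 3.6.1. One sentence in Appendix 10 would do it: state whether the Appendix 1 permanent-discontinuation criteria, including Table 8, remain in force when an abnormal value cannot be followed up. If they do, say that the interrupt-or-discontinue choice applies only to abnormalities for which Appendix 1 gives no rule. The choice of rule is for the sponsor's medical team.

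The cost is one sentence and no added procedure. The synopsis places the last visit in Q4 2023, and the SAP is dated 20 September 2023. If the protocol can no longer usefully be amended, the study report can identify any patient who met a starred pattern without a timely retest and state which action was taken. Appendix 10 already asks for pandemic-related changes in conduct to be summarised there.
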